11.5.3. Other Safety Assessments

The following safety assessments will also be performed, according to timing reported in Section 7, Schedule of Events:

- *Physical examination*: on Phase II should be performed at screening, within 7 days from treatment start, on day 1 of each treatment cycle, at EoT and at 28-days follow up. Note: at Cycle 1 Day 1, it does not need to be repeated before study drug administration if it was performed at screening within 24 hours from treatment start.
- *ECOG PS*: should be recorded at screening, within 7 days from treatment start; on day 1 of each treatment cycle (before treatment administration); at EoT and at 28-days follow up visits. Note: at Cycle 1 Day 1, ECOG PS does not need to be repeated before study drug administration if it was performed at screening within 24 hours from treatment start.
- *Weight*: should be recorded at screening, within 7 days from treatment start, and on day 1 of each treatment cycle (before treatment administration).
- *Height*: should be recorded at screening only.
- *Temperature*: should be recorded as Celsius degree, at screening within 7 days from treatment start, and on days 1, 8, 15 of each treatment cycle (before treatment administration).
- *Blood pressure and heart rate*: the assessment is mandatory, at screening within 7 days from treatment start; on days 1, 8, 15 before the treatment start and within 30 minutes after the end of infusion (before any blood samples is taken); at EoT and 28-days follow up visits. At each determination, if SBP >150 mmHg and/or DBP >95 mmHg is registered, repeat determinations two more times at 30 minutes interval.
- *Gastro-esophageal endoscopy*: should be performed to all patients with known history of gastro-esophageal varices. For these patients the assessment is mandatory, at screening within 7 days from treatment start, unless an endoscopy is available within 3 months

before the treatment start. For all other patients the assessment is not required, granted that an endoscopy is available within 24 months before the treatment start, or PI would justify the absence of clinical need for this assessment;

12-lead EC(12-lead, in triplicate, includes qualitative and quantitative assessment): the assessment is mandatory at screening, within 7 days from treatment start, at cycle 1 day 1 (first dose) and at cycle 1 day 15 (dose 3) triplicate ECG will be collected prior to dosing (30 min before the start of infusion and at least 10 minutes after any blood drawn or intravenous access procedure) and at peak concentration, prior to and as close as possible to the PK timepoint planned 5 minutes before the end of infusion (e.g. ≤ 10 minutes), and at EoT visit. It includes QT interval using Fridericia standard (QTcF) calculation. If clinically indicated, additional assessments should be done as per medical judgment. To be repeated at any time it is medically indicated. If the ECG assessment is not feasible on cycle 1 day 1 or cycle 1 day 15, a different timing or other solutions should be discussed with Sponsor. At each time point, three consecutive supine 12-lead ECGs will be performed approximately 2 minutes apart to determine mean QT interval using Fridericia standard (QTcF). The following parameters will be collected: sinus rhythm, heart rate, RR interval, PR interval, QRS interval, QT interval and QTcF interval. For all patients enrolled in the study, the Sponsor may request the ECG tracing and reports collected during the study be submitted to a third-party for retrospective independent review of the ECGs reading and interpretation.

- *AFP*: to be performed at screening, within 7 days from treatment start, at the end of even cycles at disease evaluation and at EoT. A time window of -2/+5 days is allowed.
- *Survival follow up*: the post-treatment survival status, including additional information (e.g., new anticancer therapy), will be collected at the 28-days follow up visit and thereafter every 2 months from last treatment administration until death. Telephone contacts are acceptable for these assessments.

11.6. Other Assessments

11.6.1. Blood sampling

Plasma samples will be used for pharmacokinetic evaluations of NMS-01940153 and its main metabolite NMS-03593478.

During the dose escalation part of the study (Phase I), blood samples will be collected from all patients during Cycle 1 and Cycle 2. The sample schema for pharmacokinetic (PK) collection is outlined in [Table 13](#). During the Phase II, blood samples will be collected from all patients, based on their enrollment number (odd or even), during Cycles 1, 2, 3 and 4. The sample schema for PK collection is outlined in [Table 14](#).

Blood (4 mL/timepoint) will be collected into sodium heparin Vacutainer tubes for PK analysis at the designated time. Additional blood samples for PK analysis may be collected if, in the opinion of the Investigator and of the Sponsor, an evaluation of PK parameters outside the schedule above is needed for safety reasons.

Table 13. Phase I PK Blood Sample Collection

Cycle	Day	Sample number	Sample timepoint
1	1	#1	Pre-dose
		#2	5 minutes before the end of infusion
		#3	15 minutes after the end of infusion
		#4	30 minutes after the end of infusion
		#5	1 h after the end of infusion
		#6	2 h after the end of infusion
		#7	4 h after the end of infusion
		#8	6 h after the end of infusion
		#9	8 h after the end of infusion
		#10	24 h after the end of infusion
2	3	#11	48 h after the end of infusion
	4	#12	72 h after the end of infusion
	8	#13	Pre-dose
	15	#14	Pre-dose
		#15	5 minutes before the end of infusion
		#16	15 minutes after the end of infusion
		#17	30 minutes after the end of infusion
		#18	1 h after the end of infusion
		#19	2 h after the end of infusion
		#20	4 h after the end of infusion
2	16	#21	6 h after the end of infusion
		#22	8 h after the end of infusion
		#23	24 h after the end of infusion
		#24	48 h after the end of infusion
		#25	72 h after the end of infusion
2	18	#26	168 h after the end of infusion
	22	#27	Pre-dose
	8	#28	Pre-dose
	15	#29	Pre-dose

On Phase I, during Cycle 1, the total volume of blood withdrawn for pharmacokinetic determinations from each patient will be 104 mL over 22 days (26 samples); during Cycle 2, the total volume of blood withdrawn for pharmacokinetics determinations from each patient will be 12 mL over 15 days (3 samples).

Table 14. Phase II PK Blood Sample Collection

Cycle	Day	Sample number	Enrollment number	Sample timepoint
1	1	201	All	5 minutes before the end of infusion
		202	Odd	From 15 min to 2h after the end of infusion
		203	Even	From >2h to 6h after the end of infusion
8	204	Odd	Pre-dose	
	205	Even		5 minutes before the end of infusion
15	206	All	Pre-dose	
	207	All		5 minutes before the end of infusion
	208	Even		From 15 min to 2h after the end of infusion
	209	Odd		From >2h to 6h after the end of infusion
22	210	All		At any time
2	1	211	All	Pre-dose
	15	212	All	Pre-dose
		213	All	5 minutes before the end of infusion
		214	Odd	From 15 min to 2h after the end of infusion
		215	Even	From >2h to 6h after the end of infusion
	26 or 27 or 28	216	All	At any time
3	15	217	All	Pre-dose
		218	All	5 minutes before the end of infusion
		219	Even	From 15 min to 2h after the end of infusion
		220	Odd	From >2h to 6h after the end of infusion
4	1	221	All	Pre-dose
	15	222	All	Pre-dose
		223	All	5 minutes before the end of infusion
		224	Odd	From 15 min to 2h after the end of infusion
		225	Even	From >2h to 6h after the end of infusion
	26 or 27 or 28	226	All	At any time

On Phase II, during Cycle 1, the total volume of blood withdrawn for PK determinations from each patient will be 28 mL over 22 days (7 samples); during Cycle 2, the total volume of blood withdrawn for PK determinations from each patient will be 16 mL over 26/28 days (4 samples); during Cycle 3, the total volume of blood withdrawn for PK determinations from each patient will be 12 mL over 1 day (day 15; 3 samples); during Cycle 4, the total volume of blood withdrawn for PK determinations from each patient will be 16 mL over 26/28 days (4 samples).

Details on PK samples collection, processing, storage and shipping instructions will be provided in the Study Manual.

11.6.2.1. Bioanalytical method

NMS-01940153E and its main metabolite NMS-03593478 will be assayed in plasma using a validated LC-MS/MS method. Pharmacokinetics analysis will be performed by Accelera S.r.l. (located in Italy) identified by the Sponsor as the entity in charge of samples shipment, storage and analysis.

11.6.3. Urine Sampling

Urine samples will be used for determination of the urinary excretion of the parent drug and its main metabolite.

Urine samples will be collected only during the phase I of the study, at Cycle 1, on days 1 and 15. Urine will be collected before NMS-01940153E administration and in four different portions between 0-6h, 6-24h, 24-48h, 48-72h from the start of study drug administration.

At the end of the urine collection period, for each portion, the total volume of urine will be measured, and total volume recorded in eCRF. The urine will then be mixed aliquots withdrawn for PK analysis, as outlined in [Table 15](#).

Table 15. PK Urine Sample Collection

Cycle	Day	Sample number	Sample timepoint
1	1	#1	Pre-dose
		#2	0-6h from the start of infusion
		#3	6-24h from the start of infusion
		#4	24-48h from the start of infusion
		#5	48-72h from the start of infusion
15	15	#6	Pre-dose
		#7	0-6h from the start of infusion
		#8	6-24h from the start of infusion
		#9	24-48h from the start of infusion
		#10	48-72h from the start of infusion

Additional urine samples for PK analysis may be collected if, in the opinion of the Investigator and of the Sponsor, an evaluation of PK parameters outside the schedule above is needed for safety reasons.

Details on sample collection and handling and shipping instructions will be provided in the Study Manual.

All the samples for pharmacokinetic determinations will be sent to Accelera (located in Italy), or other identified by the Sponsor as the entity in charge of samples shipment, storage and analysis.

11.6.4. Exploratory Assessments

11.6.4.1. cfDNA Sampling

For cfDNA analysis, 20 ml of peripheral blood will be collected for all patients at screening. Sponsor might decide, at any time, to stop collection of these samples based on scientific or logistic reasons.

12. STATISTICAL METHODS

12.1. Sample Size Calculation

An overall sample size of approximately 55 patients may be anticipated considering both phases of the study.

For the Phase I, approximately 12-15 treated patients may be expected. Since the trial design foresees that sequential dose-escalation steps are applied to cohorts of 3 to 6 patients up to the identification of the MTD, the number of patients who will be enrolled and treated may vary, depending upon the toxicity observed that will influence cohort size and number of dose levels tested.

For the Phase II, the investigator-assessed objective response rate by RECIST 1.1. will be the primary outcome measure.

The sample size is based on precision considerations for the estimate of the primary efficacy endpoint. A single-group design will be used to obtain a one-sided 95% lower-limit confidence interval for a single proportion. The sample proportion is assumed to be 0.3. To produce a confidence interval with a distance from the sample proportion to the lower limit of no more than 0.12, 38 patients will be needed. A lower bound of 18% for ORR by RECIST would be meaningful relative to second line therapies in HCC. The emergence of atezolizumab with bevacizumab in first line has obscured true current second line outcomes with regorafenib, lenvatinib or sorafenib but it is logical to assume second line ORR would be no better relative to the pre-atezolizumab/bevacizumab era in which sorafenib was the first line standard. Prior to the atezolizumab/bevacizumab era, regorafenib in second line showed ORR of 11% by RECIST1.1 [10] and cabozantinib 4% [22], nivolumab 15% [23], pembrolizumab 18% [24] and apatinib 10.7% [25]. Therefore, in the third line setting following failure of atezolizumab/bevacizumab in first line followed by TKI in second line, and where current third line standards are not yet defined, it is reasonable to expect historical ORR no higher than 18%. Accounting for a 10% proportion of non-evaluable patients and if the stopping rule for futility is not met, up to 43 patients could be required for completing the trial, as reported in detail in Section 12.4; however, the Phase II part of the study will not enroll beyond 40 subjects unless discussed and agreed with FDA or relevant health authority, based on emerging response rates.

12.2. Definition of Analyzed Study Populations

The following analysis sets are defined according to ICH E9 guidelines [26].

Phase I Dose Escalation

Enrolled Set (ES): this population will include all patients who are enrolled in Phase I part, regardless of whether patients receive study treatment or not. This population will be evaluated in the analysis of patients' disposition.

Treated Set (TS): this set will include all enrolled patients who take at least one dose of NMS-01940153E. This population will be evaluated in the analysis of patients' disposition, baseline characteristics, treatment exposure, safety and efficacy.

Dose-Limiting Toxicity Evaluable Set (DLTES): this set will include all patients who receive in the first cycle at least 66% of study drug, unless the reason for non-compliance is drug-related toxicity, and undergo a DLT assessment within the DLT window. Patients not fulfilling one or more of aforementioned criteria will not be considered evaluable for MTD determination and will be substituted.

Phase II

Enrolled Set (ES): this population will include all patients enrolled in Phase II, regardless of whether patients receive study treatment or not. This population will be evaluated in the analysis of patients' disposition.

Treated Set (TS): this set will include all enrolled patients who actually receive at least one dose of NMS 01940153E. This population will be evaluated in the analysis of patients' disposition, baseline characteristics, treatment exposure and safety.

Evaluable Set (ES): this is the patient population for the primary efficacy analysis. This set will include patients of the TS who have measurable disease at baseline assessed according to RECIST 1.1 and at least one tumor evaluation on treatment, unless they die before the first tumor on-treatment assessment, in which case they will be considered treatment failure. In detail, the evaluable population for primary efficacy endpoint will consist of a subset of the evaluable population up to the total number of subjects pre-determined by the interim for futility and final analyses. This means that, if the number of evaluable subjects exceeds the planned total number of subjects at either stage, the exceeding subjects will not be considered for primary efficacy analysis. Subjects will be counted into the primary evaluable population, consecutively, based on the date of first NMS-01940153E administration.

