Treated Set (TS): this set will include all enrolled patients who take at least one dose of NMS-01940153E. This population will be evaluated in the analysis of patients' disposition, baseline characteristics, treatment exposure, safety and efficacy.

Dose-Limiting Toxicity Evaluable Set (DLTES): this set will include all patients who receive in the first cycle at least 66% of study drug, unless the reason for non-compliance is drug-related toxicity, and undergo a DLT

assessment within the DLT window. Patients not fulfilling one or more of the aforementioned criteria will not be considered evaluable for MTD determination and will be substituted.

Phase II

Enrolled Set (ES): this population will include all patients enrolled in Phase II, regardless of whether patients receive study treatment or not. This population will be evaluated in the analysis of patients' disposition.

Treated Set (TS): this set will include all enrolled patients who actually receive at least one dose of NMS 01940153E. This population will be evaluated in the analysis of patients' disposition, baseline characteristics, treatment exposure and safety.

Evaluable Set (ES): this is the patient population for the primary efficacy analysis. This set will include patients of the TS who have measurable disease at baseline assessed according to RECIST 1.1 and at least one tumor evaluation on treatment, unless they die before the first tumor on-treatment assessment, in which case they will be considered treatment failure.

Primary Endpoint

Phase I Dose escalation

The primary endpoint, i.e. first cycle DLT, will be evaluated in the DLT Evaluable Set. All enrolled patients who received at least one dose of NMS-01940153E will be included in the analysis of safety.

Phase II

The primary endpoint, i.e. the ORR and its confidence interval (CI), will be evaluated in the Evaluable Set as the proportion of patients who have achieved as best overall response, confirmed complete response or partial response as defined by investigator-assessed RECIST 1.1.

Secondary Efficacy Endpoints

Objective response rate as measured by investigator-assessed mRECIST, and its CI will be provided for Phase II part only.

Duration of response, Progression Free Survival and Overall Survival will be provided for both phases. Time-to-event endpoints will be also summarized using Kaplan Meier (KM) curves and further characterized in terms of median and landmark estimates with the corresponding CI, for Phase II part only.

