20. Tumor imaging: to be performed at screening, within 28 days from treatment start (in case a tumor imaging is already available in the specified time window, it has not to be repeated); at the end of even months (even cycles) of treatment and at EoT. The EoT assessment is to be performed only if it was not performed in the previous 4 weeks. In patients withdrawn for reasons other than progressive disease (PD), during follow up, tumor assessment should be performed every 2 months, until PD or until a new antitumor therapy starts. On treatment, a time window of -2/+5 days is allowed. Patients with responding tumors (complete or partial response) must have response confirmed by CT scan at least 4 weeks after the 1 st documentation of response. The same method of assessment and technique should be used to characterize and follow the same lesion at screening, during treatment and at EoT. Ct scan is the desirable method for lesion measurement (see Section 11.3.1).
21. BCLC and TNM Staging: TNM and BCLC staging will be requested at enrollment for all patients, including collection of clinical related additional info
22. Survival follow up: post-treatment survival status, including additional information (e.g. new anticancer therapy), will be collected at the 28-days follow up visit and thereafter every 2 months from last treatment administration until death. Telephone contacts are acceptable for these assessments.
23. Biomarkers sampling: peripheral blood samples will be collected at Enrollment (≤ 7 days before Cycle1 Day1) for analysis of selected molecular alterations in circulating free DNA (cfDNA) from plasma
24. PK blood sample: during the Phase II, a sparse sampling procedure will be adopted; blood sampling for PK is to be performed at cycles 1, 2, 3 and 4 (refer to Table 5 for details).
25. End of Treatment (EoT): visit to be performed within 7 days from the decision of discontinuing the study drug.
26. Off treatment assessments: 28 days, and no more than 35 days, after discontinuation of study treatment patients will return for the following assessments: ECOG PS, blood pressure and heart rate, hematology, blood chemistry, coagulation, concomitant medications, adverse events and survival follow up. Further follow up contacts will be scheduled every 2 months from last treatment administration, until death, to assess the survival status, including possible additional information.

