9.2.3.2. Re-treatment Criteria and Cycle Delay

A new cycle of treatment may begin when hematological and non-hematological toxicities are Grade ≤ 1 or have recovered to baseline values.

If these conditions are not met, treatment should be delayed for 1 week to allow for recovery. If, after 1-week delay, re-treatment criteria are met, then the new cycle can be initiated with a starting dose defined based on the toxicities observed in the previous cycle as outlined in the [Table 6](#).

If, after this period, toxicities do not recover to the pre-defined level, the patient will be withdrawn from the treatment, unless the Investigator believes treatment continuation is in the patient best interest. In this case, a maximum delay of 2 weeks (up to day 42 from cycle start) will be allowed.

Table 6. Dose Reductions/Treatment Discontinuations for NMS-01940153E Based on the Worst Grade (as per NCI CTCAE Criteria, Version 5.0) Observed During a Treatment Cycle and in the Prior Treatment Cycle

Toxicity	Dose Adjustment during treatment cycle	Next cycle Starting Dose
Hematological Toxicities		
Neutropenia Grade 3	Omit dose; when resolved to \leq Grade 1 within the same cycle, decrease one dose level.	Start at or maintain the decreased dose level.
Neutropenia Grade 4	Omit dose; when resolved to \leq Grade 1 within the same cycle, decrease one dose level.	Start at or maintain the decreased dose level.
Febrile Neutropenia	Omit dose; when resolved, decrease one dose level.	Start at or maintain the decreased dose level.
Thrombocytopenia Grade 3 associated with bleeding or thrombocytopenia Grade 4	Omit dose; when resolved to \leq Grade 2 within the same cycle, decrease one dose level.	Start at or maintain the decreased dose level.
Anemia Grade 3	Omit dose; when resolved to \leq Grade 2 within the same cycle, decrease one dose level.	Start at or maintain the decreased dose level.
Anemia Grade 4	Study treatment discontinuation.	Study treatment discontinuation.
Other Grade 3 Hematologic Toxicities	Omit dose; when resolved to \leq Grade 2 within the same cycle, decrease one dose level.	Start at or maintain the decreased dose level.
Other Grade 4 Hematologic Toxicities	Study treatment discontinuation.	Study treatment discontinuation.
Nausea and/or Vomiting		
Grade \geq 3 despite optimal management of the event §‡	Omit dose; when resolved to \leq Grade 2 within the same cycle, decrease one dose level.	Start at or maintain the decreased dose level.
Diarrhea		

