11.3.1. Tumor Imaging

Baseline tumor imaging (by CT scan, PET or MRI) has to be performed at screening within 28 days prior to the treatment start. On treatment, tumor assessments will be performed every even month (i.e., end of Cycle 2, 4, 6 etc) or whenever a clinical deterioration is observed and at the end of last cycle, unless a tumor assessment was performed within the previous 4 weeks. In patients withdrawn for causes other than disease progression, during follow up, regular tumor imaging assessments will be performed every 2 months, until PD or until a new antitumor therapy starts. On treatment, a time window of -2/+5 days is allowed.

Patients with responding tumors (complete or partial response) must have response confirmed at least 4 weeks after the first documentation of response.

CT scan is the desirable method for lesion measurement. MRI is acceptable provided that the size of the measurable lesion is twice the slice thickness of the MRI. MRI should be performed at pre-treatment in case of known or suspected CNS involvement.

According to RECIST, the same method and technique (CT scan or MRI) should be used to characterize each identified and reported lesion at baseline and during the following assessments.

Imaging-based evaluation should be preferred to clinical examination when both could be used to assess the antitumor effect of the treatment.

According to mRECIST, tumor assessment should be performed with the administration of intravenous contrast to obtain a dual-phase imaging of the liver. To prevent possibly allergic reactions to intravenous Contrast Medium (CM), patients with previous reaction(s) to CM, asthma even drug controlled and/or food or drug allergies will be treated with a premedication (corticosteroid).

Patients can be followed with either contrast-enhanced spiral CT (preferably with use of multi-slice scanners) or contrast-enhanced dynamic MRI. Each modality has advantages and disadvantages, and mRECIST does not recommend one modality over another.

However, it is recommended that the same imaging modality be used throughout the study. Ultrasound – including contrast-enhanced ultrasound – is not recommended for the general use of mRECIST.

PET/CT is not accepted for treatment assessment in guidelines.

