11.3.1.10. Best Overall Response

The best overall response is the best response recorded from the start of the study treatment until the end of treatment taking into account any requirement for confirmation (achievement of both measurement and confirmation criteria, depending on the nature of the study and the protocol requirement). The patient's best overall response assignment will depend on the findings of both target and non-target disease and will also take into consideration the appearance of new lesions.

Table 11. Best overall response when confirmation of CR and PR required

Overall response First time point	Overall response Subsequent time point	BEST overall response
CR	CR	CR
CR	PR	SD, PD or PR ^a
CR	SD	SD provided minimum criteria for SD duration met, otherwise, PD
CR	PD	SD provided minimum criteria for SD duration met, otherwise, PD
CR	NE	SD provided minimum criteria for SD duration met, otherwise NE
PR	CR	PR
PR	PR	PR
PR	SD	SD
PR	PD	SD provided minimum criteria for SD duration met, otherwise, PD
PR	NE	SD provided minimum criteria for SD duration met, otherwise NE
NE	NE	NE

CR = complete response, PR = partial response, SD = stable disease, PD = progressive disease, and NE = not evaluable.

^a If a CR is truly met at first time point, then any disease seen at a subsequent time point, even disease meeting PR criteria relative to baseline, makes the disease PD at that point (since disease must have reappeared after CR). Best response would depend on whether minimum duration for SD was met. However, sometimes 'CR' may be claimed when subsequent scans suggest small lesions were likely still present and in fact the patient had PR, not CR at the first time point. Under these circumstances, the original CR should be changed to PR and the best response is PR.

In some circumstances, it may be difficult to distinguish residual disease from normal tissue. When the evaluation of a CR depends upon this determination, it is recommended that the residual lesion be investigated by fine needle aspirate or biopsy before assigning a status of CR.

For equivocal findings of progression (e.g., very small and uncertain new lesions; cystic changes or necrosis in existing lesions), treatment may continue until the next scheduled assessment. If at the next scheduled assessment, progression is confirmed, the date of progression should be the earlier date when progression was suspected.

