Evaluable Set (ES): this is the patient population for the primary efficacy analysis. This set will include patients of the TS who have measurable disease at baseline assessed according to RECIST 1.1 and at least one tumor evaluation on treatment, unless they die before the first tumor on-treatment assessment (i.e. if the patients died within 61 days from the start of the treatment considering that the first on treatment tumor assessment is foreseen at the end of cycle 2 with a time window of -2/+5 days), in which case they will be considered treatment failure. Moreover, subjects must have disease relapsed or refractory to the standard of care treatment including an immunocheckpoint inhibitor as first line and at least a tyrosine kinase inhibitor, not exceeding 3 lines of prior systemic treatment. Patients who received the RP2D defined in phase I portion as starting dose and from cycle 2 a dose increment of 25% (as per protocol version 4.0 dated 30-Jun-2022) were considered not evaluable for efficacy analysis (intra-patient dose escalation no more applicable as per protocol version 5.0). In detail, the evaluable population for primary efficacy endpoint will consist of a subset of the evaluable population up to the total number of subjects pre-determined by the interim for futility and final analyses. This means that, if the number of evaluable subjects exceeds the planned total number of subjects at either stage, the exceeding subjects will not be considered for primary efficacy analysis. Subjects will be counted into the primary evaluable population, consecutively, based on the date of first NMS-01940153E administration.

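### The Phase II primary set drops treated patients who stop alive and unscanned, no required analysis shows the effect on ORR, and the SAP's 61-day death limit does not match the protocol

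*Protocol*

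**What the plan says.** **Primary set.** Protocol 12.2 defines the Phase II Evaluable Set as treated patients with "measurable disease at baseline assessed according to RECIST 1.1 and at least one tumor evaluation on treatment". Synopsis 1.4 carries the same condition and its only exception: "at least one tumor evaluation on treatment, unless they die before the first tumor on-treatment assessment". Such deaths count as treatment failures, and neither place sets a time limit. Both documents cap the primary set at the planned number of evaluable patients (38), counted by date of first dose.

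**SAP version.** SAP section 7 keeps the definition but applies the death exception "if the patients died within 61 days from the start of the treatment". It explains the figure by the end-of-cycle-2 scan and its window of -2/+5 days. It also requires the Phase II prior-therapy history, and excludes patients whose dose was raised by 25% from cycle 2 under protocol version 4.0.

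**Response window and scans.** Protocol 11.3.1.10 states: "The best overall response is the best response recorded from the start of the study treatment until the end of treatment". Scans fall at the end of even cycles and, under Protocol 11.3.1, "whenever a clinical deterioration is observed and at the end of last cycle, unless a tumor assessment was performed within the previous 4 weeks". Phase II footnote 20 in Protocol section 7 says: "The EoT assessment is to be performed only if it was not performed in the previous 4 weeks".

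**Cycle delay.** Under Protocol 9.2.3.2 a new cycle may be put off by one week. If the investigator judges continuation to be in the patient's interest, "a maximum delay of 2 weeks (up to day 42 from cycle start) will be allowed".

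**Other analyses.** Protocol 12.3.4 and SAP 9.7 leave Phase II efficacy on the Treated Set to discretion, as supportive only. Protocol 12.3.4.2 and SAP 9.7.2 put Phase II DoR, PFS and OS on the Evaluable Set. SAP 9.2 lists patients excluded from efficacy analysis individually.

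**The concern.** ORR is the primary endpoint of an uncontrolled trial and is read against a historical 18%. Patients who leave early for toxicity, withdrawal of consent or loss to follow-up, without a scan, are certain non-responders on the plan's own definition. Removing them moves the estimate in one direction only. The analysis that would reveal the shift can be chosen or skipped after the results are known.

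The death rule is a separate matter. The two documents can classify the same patient differently, as a failure in the denominator or as not evaluable. The primary denominator then depends on which document is followed.

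OS needs no scan at all, so conditioning it on one is an avoidable selection. For OS and PFS the direction of that selection is not fixed.

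**Working it through.** **1. The plan's own figure.** Inputs from Protocol 12.1: assumed ORR 0.30, one-sided 95% lower limit, distance at most 0.12. The exact (Clopper-Pearson) lower limit is the 0.05 quantile of Beta(x, n - x + 1). With x = 0.3n, n = 37 gives a distance of 0.1212 and n = 38 gives 0.1197, so 38 is reproduced. Allowing 10% non-evaluable: 38/0.9 = 42.2, rounded up to 43. Enrolment is capped at 40 unless a health authority agrees otherwise.

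**2. Direction.** Let r be responders, n treated and k unscanned. Best overall response is counted only to the end of treatment, and CR or PR needs confirmation at least 4 weeks later, so an unscanned patient adds nothing to r. Dropping k patients changes r/n to r/(n - k), which is never smaller. The ratio is 1/(1 - d), with d = k/n:
- 0 of 40: 1.00
- 2 of 40: 40/38 = 1.05
- 4 of 40: 40/36 = 1.11

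**3. Against the 18% reference (one-sided exact 95% lower limits).**

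| Unscanned | Evaluable | Same responders over all 40 |
|---|---|---|
| 2 of 40 | 12/38 = 31.6%, limit 19.3% | 12/40 = 30.0%, limit 18.3% |
| 4 of 40 | 11/36 = 30.6%, limit 18.2% | 11/40 = 27.5%, limit 16.3% |

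The smallest responder count with a limit of at least 18% is 12 at every n from 37 to 40 and 11 at n = 36. The reading therefore changes only when 4 or more of 40 are unscanned.

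SAP 9.7.1 does not say whether its 95% interval is one-sided or two-sided. If it is two-sided, 12/38 has a limit of 17.5%, already below 18%. The count needed is then 13 at n = 38 to 40 and 12 at n = 36 or 37, so the reading changes with 3 or more of 40 unscanned (12/37 18.0%, 12/40 16.6%).

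**4. The 61-day limit.** Latest first scan = length of cycle 1 + 28 + 5:
- no delay: 28 + 28 + 5 = 61, the SAP's figure
- cycle 1 to day 35: 35 + 28 + 5 = 68
- cycle 1 to day 42: 42 + 28 + 5 = 75

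Take a patient whose cycle 1 ran to day 42. The scan is scheduled for day 70, with a window of day 68 to day 75. If this patient dies on treatment and unscanned on day 65, the scan is not yet due. The protocol counts a failure; the SAP excludes the patient.

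**5. Size of one reclassified patient.** With 38 evaluable under the protocol, one such death and no replacement available, 12 responders give 12/38 = 31.6% (limit 19.3%) under the protocol and 12/37 = 32.4% (19.9%) under the SAP.

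**The case against.** A prespecified response-evaluable set that counts early deaths as failures, with a sample-size allowance for non-evaluable patients, is a legitimate choice in a design the synopsis calls exploratory. That stands, and it is why the primary set need not change.

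The scan gap is also narrow. For a patient never scanned on treatment, the 4-week waiver can rest only on the screening scan, so it covers only very early stoppers. Others should have an end-of-treatment or deterioration scan unless it is missed. Neither document says whether an end-of-treatment scan counts as on treatment; the separate TLG appendix, not available here, may. No unscanned rate is documented, and the group may be empty.

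The listings would let someone rebuild the effect by hand. That is true, but they give no ORR or interval, and nothing requires one.

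A reader might infer that the two death rules give very different denominators, for example 40 against 37 if four unscanned patients all die before the final analysis. The documents do not support this. The primary set is capped at 38 evaluable patients. The inference also needs every later death, even long after stopping, to count as death before the first on-treatment scan. On that reading most patients who stop alive and unscanned would eventually return as failures, and the exclusion would largely disappear under the protocol. The conflict that remains is the narrow one in step 4.

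**Conclusion.** The point holds in two limited parts.

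- **Missing scans.** Dropping patients who stop alive and unscanned cannot lower the primary ORR, and no mandatory analysis shows by how much it rises. With 2 of 40 unscanned the one-sided limit stays above 18%. Crossing needs about 4 of 40, which assigns the whole 10% non-evaluable allowance to missing scans; that is an assumption.
- **Death rule.** The SAP's 61-day limit conflicts with the protocol's unlimited rule and overlooks permitted cycle delay. The effect is about one patient at a time, but the text is inconsistent whatever the count.

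Two further inferences should be resisted. The 18% is a reference for interpretation, not a success rule, so crossing it does not turn a failed trial into a positive one. The one-way direction belongs to the missing-scan step alone: the SAP's exclusions for version 4.0 dose escalation and prior therapy, and the cap on evaluable patients, could remove responders, so the full Evaluable-versus-Treated difference has no fixed sign.

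Severity: minor to should-fix.

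**What to change.** 1. **Death rule.** Reconcile SAP section 7 with Protocol 12.2 and synopsis 1.4 by replacing the fixed 61 days with each patient's own scheduled end-of-cycle-2 scan date, including any permitted delay and the +5-day window. Use the same wording in all three places.
2. **Supportive ORR.** In Protocol 12.3.4 and SAP 9.7, replace the discretionary wording with a mandatory supportive ORR with exact limits. Use treated patients with measurable baseline disease, first dosed no later than the last patient in the primary set, and count those without an on-treatment scan as non-responders. Show it with and without the patients the SAP excludes for version 4.0 dose escalation or prior therapy, so that the effect of missing scans is isolated. The primary set is unchanged.
3. **OS and PFS.** In Protocol 12.3.4.2 and SAP 9.7.2, report OS, and PFS as supportive, on the Treated Set as well, with the same with/without split. Keep the Evaluable Set analyses.

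The cost is wording in both documents and a few extra tables from data already collected. No extra patients, visits or scans are needed.
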